14.2. Post randomisation discontinuations

Information on participant withdrawal can be found in section 5.4 of the protocol. Before the

PICC has been inserted, parents are free to withdraw from any aspect of the trial, however once the PICC has been inserted, it will only be removed for clinical reasons only.

Withdrawals from follow-up and data collection will be recorded and presented descriptively

along with any reasons given.

15. Protocol Deviations

Possible protocol deviations will be specified as minor or major in the Trial Monitoring Plan.

Protocol deviations are classified prior to requesting the treatment allocations and any analysis

being performed. The number (and percentage) of babies with at least one protocol deviation

will be summarised overall and by treatment group. Details will also be presented on the

number of babies with at least one major/minor protocol deviation. The babies that are

included in the intention to treat (ITT) analysis data set will be used as the denominator to

calculate the percentages. No formal statistical testing will be undertaken.

Babies to be excluded from analysis populations need to be defined in template ST001TEM04:

Protocol deviations and data set definitions template agreed and approved prior to any release

of randomisation code.

16. Unblinding

N/A as PREVAIL is an open label study. No details on unblinding will be presented.

17. Efficacy Evaluations

17.1. Data Sets Analysed

The principle of intention-to-treat, as far as practically possible, will be the main strategy of the

analysis adopted for all efficacy outcomes. These analyses will be conducted on all

randomised participants, in the group to which they were allocated, and for whom the

outcome(s) of interest have been observed/measured.

The membership of the analysis set for the efficacy outcomes will be determined and

documented and any reason for participant exclusion will be given prior to the blind being

broken and the randomisation lists being requested. Reasons may include missing data, loss

to follow up.

The numbers included in the ITT and safety populations (described in section 20.1) will be

presented in a table.

17.2. Demographic and Other Baseline Characteristics

The comparability of the two randomised groups with respect to the baseline clinical factors

of the following will be presented

Gender

Birth weight in grams (categories of <750, 750 – <1000, 1000 - <1250, 1250 –

<1500, 1500 - <1750, 1750 - < 2000 and ≥2000)

- Gestational age in weeks (categories of <26, 26 <28, 28 <30, 30 <32, 32 <34, 34 <36, 36 <38, ≥38). Note: This will be estimated by calculating the difference in weeks between the baby's date of birth and final estimated date of delivery. It will be assumed that the final estimated date of delivery will be 40 weeks. Weeks are complete weeks, for example "36 weeks" would mean 36 weeks plus anything up to and including 6 days.
- Major congenital anomaly
- Age at randomisation in days (categories of <2, 2 <7, 7 <14,, 14 < 21, 21 < 28 ≥28). Note: "<2 days" = "<48 hours".
- Location of birth (categories of 'inborn' and 'Baby transferred to the study hospital after birth)
- Mode of delivery (categories of 'vaginal' and 'caesarean')
- Membranes ruptured more than 24 hours before delivery (Yes/No)
- Apgar score at 5 minutes (categories of 0 3, 4 7, 8 10)
- Maternal antenatal corticosteroids (Yes/No)
- Maternal antibiotics within 12 hours prior to delivery (Yes/No)
- Surgery before randomisation (categories of 'longer than 6 days ago', 'within the last 6 days' and 'no surgery'
- Positive blood culture within 72 hours prior to randomisation (Yes/No) taken from microbiology form
- Antibiotics or antifungals within 72 hours prior to randomisation excluding Prophylaxis (Yes/No). Note: See table below for details on classifying this from information in section 5 of CRF "Form 3: Baby Characteristics"

Questions on Form 3:	Baby classified as		
1: IV antibiotics	2: IV and/or enteral	2a: If yes, was the	having "Antibiotics
within 72 hours prior	antifungal	antifungal for	or antifungals within
to randomisation?	medication within 72	prophylaxis only?	72 hours prior to
	hours prior to		randomisation"
	randomisation?		
Yes	Yes	No	Yes
Yes	Yes	Yes	Yes
Yes	No	N/A	Yes
No	Yes	No	Yes
No	Yes	Yes	No
No	No	N/A	No

Number of devices in situ at randomisation (<4, ≥4)

Respiratory support (categories of 'None', 'ET Tube', 'Non-invasive ventilation', and

'Oxygen')

PICC insertion site (categories of 'No line inserted', 'Lower limb', 'Upper limb', 'Scalp',

'Other').

All comparisons between the groups will be descriptive in nature and no formal hypothesis

testing will be performed. Categorical variables in each group will be summarised by counts

(percentages) while continuous variables will be summarised by measures of central

tendency (mean, standard deviation (SD), range, median, interquartile range (IQR)).

17.3. Presentation of data for treatment adherence

Tables mentioned within this section will be presented overall and split by treatment.

Frequency tables (with percentages) will be presented for:

Reasons for PICC removal

• The number of babies whose PICC was removed less than 24 hours after

randomisation

The number of babies receiving the allocated PICC

The number of babies receiving a non-allocated PICC

The number of babies randomised but did not receive any PICC

The type of sample and whether an e-test was performed for positive cultures

• Length of time PICC is in situ for (from insertion to removal).

17.4. Analysis of outcomes

17.4.1. Primary Outcome

The primary efficacy outcome is time to BSI based on any positive blood/CSF culture

(including fungal isolates) taken between 24 hours after randomisation until 48 hours after

PICC removal.

17.4.1.1. **Derivation**

The date and time that a sample was taken is recorded on CRF "Form 5: Microbiology". The

samples included for the primary outcome are those taken between 24 hours after

randomisation until 48 hours after PICC removal. The date and time of randomisation can be

found on CRF "Form 2: Randomisation". The date and time of PICC removal can be found on

CRF "Form 6: Removal". The unit of measurement will be hours.

BSI is defined as any positive culture recorded on CRF "Form 5: Microbiology" for the field

"organism cultured" (any culture except an entry of 'none') from blood or CSF samples. Any

'other' recorded organism will be referred to the clinical team for confirmation of whether this

is a positive culture. Organisms grown from 'other' sample types will also be referred to the

clinical team for confirmation of whether this constitutes the primary outcome.

All decisions made by the clinical team, will be made blinded to treatment allocation.

If there is a positive culture prior to the primary outcome time window and a positive culture in

the primary outcome time window:

• If the second positive culture is from the same isolate as the first and:

o there were less than 14 days between the two samples they should be

classified as the same episode of BSI and the positive culture within the primary

outcome time window will not be counted.

o there were 14 days of more between the two samples they should be classified

as two independent episodes of BSI and the positive culture within the primary

outcome time window will be counted.

If the second positive culture is from a different isolate to the first and:

o there were less than 24 hours between the two samples they should be

classified as the same episode of BSI and the positive culture within the primary

outcome time window will not be counted.

o there were 24 hours or more between the two samples they should be classified

as two independent episodes of BSI and the positive culture within the primary

outcome time window will be counted.

If there are multiple positive cultures within the primary outcome time window, each positive

culture will be assessed using the criteria above and the first one that meets the definition will

be counted.

Survival times will be measured from the date and time of randomisation to the date and time

of the first sample, that meets the definition of independent episode of BSI outlined above.

For those not experiencing the primary outcome, they will be censored at death (date and time

found on Form 7a: Clinical Outcomes under section 1 question 3), 48 hours after PICC

removal or for those with no PICC inserted, 48 hours after randomisation. All censoring will be

assumed to be non-informative.

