17.5.3. Type of organism isolated from BSI

17.5.3.1. Derivation

BSI is defined as in section 17.4.1.1. If there are multiple positive cultures within the primary

outcome time window, each positive culture will be assessed using the criteria in section

17.4.1.1 and the following (comparing positive cultures within the POTW as well as comparing

to positive cultures prior to POTW):

If the second positive culture is from the same isolate as the first and

there were less than 14 days between the two samples they should be

classified as the same episode of BSI.

o there were 14 days of more between the two samples they should be

classified as two independent episodes of BSI.

• If the second positive culture is from a different isolate to the first and

there were less than 24 hours between the two samples they should be

classified as the same episode of BSI.

o there were 24 hours or more between the two samples they should be

classified as two independent episodes of BSI.

The type of organism can be found on CRF "Form 5: Microbiology" under "Organism cultured".

Where a sample grows 3 or more different organisms, it is recorded as mixed growth rather

than as the individual organisms.

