17.5.5. Occurrence of 1 or more BSI

17.5.5.1. Derivation

BSI is as defined in section 17.4.1.1. Where there are multiple positive cultures in the POTW,

independent episodes of BSI will be classified as in section 17.5.3.1. If a baby has one or

more independent episodes of BSI within the POTW then this is classed as 'Yes'.

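### The primary-outcome rule tests window cultures only against pre-window cultures, so a repeat of an episode it has just excluded can become the primary event, and one reading of section 17.5.3.1 would not count it

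*SAP*

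**What the plan says.** **Window.** In SAP section 17.4.1.1 the "samples included for the primary outcome are those taken between 24 hours after" randomisation and 48 hours after PICC removal. The pre-window period therefore includes the first 24 hours after randomisation.

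**Episode rule for the primary outcome.** The trigger is stated once: "If there is a positive culture prior to the primary outcome time window and a positive culture in" the window. For the same isolate, if "there were less than 14 days between the two samples they should be" treated as one episode, the window culture does not count; at 14 days or more it does. For a different isolate, if "there were less than 24 hours between the two samples they should be" treated as one episode, it does not count; at 24 hours or more it does. When the window holds several positives, each positive "culture will be assessed using the criteria above and the first one that meets the definition will" be the event.

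**Episode rule for the secondary BSI outcomes.** Section 17.5.3.1 applies the criteria in section "17.4.1.1 and the following (comparing positive cultures within the POTW as well as comparing" with those before it. Section 17.5.4.1 (BSI rate) uses this rule. So does section 17.5.5.1 (occurrence of 1 or more BSI), where "independent episodes of BSI will be classified as in section 17.5.3.1".

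**The concern.** The rule in 17.4.1.1 exists to keep episodes that began before the window out of the primary outcome. Because its only comparators are pre-window cultures, a window culture that has been excluded plays no further part. A later culture of the same isolate can then pass the limit against the pre-window culture alone and become the event, hours or days after its predecessor was ruled out. The within-window comparison in 17.5.3.1 is worded as an addition, which confirms that 17.4.1.1 lacks it.

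Three things are at stake.

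- To the extent that such repeats continue an episode neither catheter could have prevented, they add events unrelated to treatment and on average pull the hazard ratio towards 1.
- The primary outcome and the occurrence outcome cover the same window and start from the same definition of BSI, yet could classify one baby differently.
- The four primary sensitivity analyses (19.1.1 to 19.1.4) take BSI as defined in 17.4.1.1, so none of them tests the rule. Section 21 has a second statistician program the primary analysis independently from this text, so an unclear rule invites two codings.

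**Working it through.** The SAP gives no figure on this point to reproduce. The check applies both rules as written to example sequences. Times are hours from randomisation, the window opens at +24 h, and X and Y are different isolates.

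**Sequence A, same isolate: X at −48 h, X at +240 h, X at +312 h.**

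- 17.4.1.1, second culture: 240 − (−48) = 288 h = 12 days, under 14, excluded.
- 17.4.1.1, third culture: 312 − (−48) = 360 h = 15 days, at least 14, **counted as the primary event**.
- Third against second culture: 312 − 240 = 72 h = 3 days, under 14, same episode. Only 17.5.3.1 makes this comparison.

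**Sequence B, different isolate: X at +10 h, Y at +30 h, Y at +40 h.**

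- 17.4.1.1, first Y: 30 − 10 = 20 h, under 24, excluded.
- 17.4.1.1, second Y: 40 − 10 = 30 h, at least 24, **counted as the primary event**.
- Second Y against first Y: 40 − 30 = 10 h, under 14 days, same episode. Again only 17.5.3.1 makes this comparison.

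**Two readings of 17.5.3.1.** Its limits are pairwise, and it does not say which earlier culture is the comparator.

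| Sequence | 17.4.1.1 | 17.5.3.1, any earlier positive | 17.5.3.1, first culture of each episode |
|---|---|---|---|
| A | event at +312 h | no window episode | episode at +312 h |
| B | event at +40 h | no window episode | episode at +40 h |

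**Direction.** All sequences of one pre-window and two window cultures were enumerated in 6-hour steps, with an assumed pre-window span from 72 h before to 24 h after randomisation and an assumed 21-day window. There are 16 pre-window times, 84 × 83 / 2 = 3,486 pairs of window times and 5 isolate patterns: 16 × 3,486 × 5 = 278,880 sequences.

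- Against the any-earlier reading, 23,520 sequences count under 17.4.1.1 but not under 17.5.3.1, and 0 the other way round.
- Against the first-culture reading, 0 sequences count under 17.4.1.1 but not under 17.5.3.1.
- With no pre-window positive, 0 sequences differ.

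These are counts of possible patterns, not expected frequencies.

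**Size, on assumed inputs.** Only the 858 babies come from the SAP (8.4). Assume that 5–15% have a pre-window positive, that 5–10% of those have a run of cultures like A or B, and that 10–20% of all babies have another primary event.

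- Affected babies: 858 × 0.05 × 0.05 = 2.1, up to 858 × 0.15 × 0.10 = 12.9; about 2 to 13.
- Other events: 858 × 0.10 = 86, up to 858 × 0.20 = 172.
- Share of counted events: 2/(172 + 2) = about 1%, up to 13/(86 + 13) = about 13%.

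The upper end combines the most extreme assumptions.

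**The case against.** **The two sections need not conflict.** In sequence A, 17.5.3.1 makes the third culture independent of the first and the same episode as the second, and it gives no tie-break. If comparison is with the first culture of each episode only, both sections give the same answer. This stands: a reader might infer that the SAP plainly contradicts itself, but the text supports only a conditional conflict. What remains is that 17.5.3.1 does not state the first-culture reading.

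**The counted culture is not shown to be a false event.** A reader might infer that infection present before the catheter could act is charged to the catheter. Sequence B does not show that: Y first grows inside the window, and its exclusion because X grew 20 hours earlier is a convention. The pre-window period also includes 24 hours after randomisation, when the PICC may already be in place. The counted culture also meets the headline definition of a positive culture in the window. All this stands. The fault is narrower: the rule assigns Y to a pre-window episode and then counts Y again as new.

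**The primary outcome needs only a first event.** That is a plausible reason for a shorter rule, and babies with no pre-window positive are indeed unaffected. It does not explain why an excluded culture ceases to be a comparator.

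**The case is probably rare and affects both arms alike.** Sequence A needs three suitably spaced positives before the window closes. Removal for infection, one of the recorded removal reasons (8.4.3), would close it early in some babies. This stands, and it limits the severity. Some babies with a pre-window positive are nevertheless foreseen: section 17.2 lists a positive blood culture in the 72 hours before randomisation as a baseline characteristic.

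**Conclusion.** The concern holds in limited form. As written, 17.4.1.1 can make a repeat of an already excluded isolate the primary event. Whether that disagrees with the occurrence outcome depends on a choice of comparator that 17.5.3.1 leaves open: under the any-earlier reading the same baby can be a primary event and a No for occurrence, and under the first-culture reading the results agree.

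In the sequences tested, the difference only ever added primary events. The number is unknown and probably small; 2 to 13 events, or about 1% to 13% of those counted, rests entirely on the assumed inputs. Any systematic effect would be dilution of the hazard ratio. With few babies involved, chance imbalance could move it either way. The documents do not support a claim that the primary result would be materially biased.

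This should be fixed because it concerns the event definition of the primary outcome and the repair is cheap. It does not make the planned analysis unusable.

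**What to change.** Before allocations are requested, put one time-ordered episode rule in 17.4.1.1 and refer 17.5.3.1, 17.5.4.1 and 17.5.5.1 to it:

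1. Take all positive cultures in time order, before and inside the window, and assign each to an episode using the existing 14-day and 24-hour limits.
2. Keep excluded cultures as comparators. A repeat of an isolate already assigned to a pre-window episode is then not a primary event within the 14-day limit.
3. State whether the 14 days run from the first or the latest culture of that isolate in the episode. Running from the latest without a cap would chain indefinitely: an isolate recurring every 13 days would never count. Sequence B is not an event under either choice. Sequence A is an event if the limit runs from the first culture and not if it runs from the latest. State the starting culture for the 24-hour limit too.
4. Give a tie-break for a culture that matches two episodes, for example an X less than 14 days after a pre-window X and less than 24 hours after an independent window Y.

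The cost is a paragraph of SAP text and a small change to the derivation program, with no new data. The downside is that a few primary events may be removed. Settling the rule before allocations are known matters because the trial is open label and a later choice would be open to challenge.

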17.4.1.2. Analysis

The following will be reported overall and split by sample type and treatment:

• Number of babies with sample taken in primary outcome time window (24 hours after

randomisation and up to 48 hours after PICC removal)

Number of samples taken in primary outcome time window

Number of babies with BSI in the POTW

This is a time to event outcome and will be analysed using the log-rank test and Kaplan-Meier

curves presented with the numbers at risk for each treatment group. The median and

interquartile range for time to BSI will be presented.

Cox proportional hazard regression models will be used if appropriate. However, since the

hazard of infection may not be constant post CVC insertion, non-proportional hazards survival

models will also be investigated. Results will be presented using Hazard Ratios and 95%

confidence intervals, along with the log-rank p-value.

Differences between date and time of randomisation and date and time of insertion will be

summarised using medians and IQR.

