8.4. Patient population studied

The trial population aims to include 858 babies who require the narrowest PICC (Premicath 1

French gauge (Fr)).

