8.7. Method of assignment to treatment

Full details of the randomisation procedure can be found in sections 6.3 and 9.2 of the protocol.

The randomisation list will be generated by a statistician (who is not involved with the PREVAIL

trial) at the CTU. Babies will be randomised to AM-PICC or S-PICC in a ratio of 1:1.

Randomisation will be stratified by centre. Babies will be randomised using a secure (24-hour)

web based randomisation programme controlled centrally by the CTU to ensure allocation

concealment. Details of block sizes can be found in the Statistics Trial File under section 4.

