9.2. Secondary outcomes

Outcomes captured up until 48 hours after PICC removal:

1. Rifampicin resistance in any isolate from blood/CSF culture.

2. Rifampicin resistance in any isolate from PICC tips.

3. Type of organism isolated from BSI.

4. Rate of BSI per 1000 PICC-days (including recurrent BSI).

5. Occurrence of 1 or more BSI.

6. Rate of catheter-related BSI per 1000 PICC days.

7. Rate of blood/CSF culture sampling per 1000 PICC days.

8. Duration of antimicrobial exposure from randomisation up to 48 hours after PICC

removal.

9. Time to PICC removal.

Outcomes captured up until discharge home from neonatal care/death/6 months post

randomisation:

10. Chronic lung disease 36 weeks postmenstrual age.

11. Necrotizing enterocolitis (NEC): Bell's stage II or III.

12. Treatment for retinopathy of prematurity.

13. Abnormalities on cranial ultrasound.

14. Time to full milk feeds after randomisation.

15. Total duration of parenteral nutrition from randomisation until discharge from NNU.

16. Death:

a) within 6 months (26 weeks) of randomisation

b) before discharge home from neonatal care

c) time to death

10. Determination of Sample Size

The sample size calculation can be found in section 9.4 of the protocol.

11. Study Framework

The overall objective for each of the study outcomes (primary and secondary) is to test the

superiority of AM-PICCs compared with S-PICCs.

12. Confidence Intervals, p-values and Multiplicity

All applicable statistical tests will be two-sided and will be performed using a 5% significance

level; confidence intervals presented will be 95%. No adjustment will be made for multiplicity

for the secondary outcomes. Percentages will be presented as 1 decimal place. Test statistics,

p-values, confidence intervals and measures of spread will be presented as 2 decimal places.

13. Timing and Objectives of Interim and Final Analyses

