17.5.5.2. Analysis

The analysis will use the method of Fisher's exact test to compare proportions in the standard

group compared to the impregnated group and relative risks will be presented with 95%

confidence intervals.

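### Randomisation is stratified by centre and plausible predictors of BSI are recorded, but the primary, sensitivity and binary analyses use neither; the tests stay valid but may lose some power

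*SAP*

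**What the plan says.** On the design, SAP section 8.7 states: "Randomisation will be stratified by centre". Centre is the only stratification factor named.

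On the primary analysis, section 17.4.1.2 states: "This is a time to event outcome and will be analysed using the log-rank test and Kaplan-Meier" curves. Cox models follow if appropriate, and non-proportional-hazards models will be explored. No centre term, stratum, frailty or baseline covariate is named. The four primary sensitivity analyses (sections 19.1.1 to 19.1.4) change the event definition, the samples counted or the time origin. None adds strata or adjustment.

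On binary outcomes, section 17.5.5.2 uses Fisher's "exact test to compare proportions in the standard" group with the impregnated group, plus a relative risk. The same unstratified method serves chronic lung disease, NEC, retinopathy treatment, cranial ultrasound abnormality, death and rifampicin resistance.

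On baseline data, section 17.2 limits use to description: "The comparability of the two randomised groups with respect to the baseline clinical factors" listed there will be presented. The list includes gestational age, birth weight, age at randomisation, devices in situ and a positive blood culture in the preceding 72 hours.

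**The concern.** Blocking within centre removes between-centre variation from the treatment comparison. An unstratified test still counts that variation in its variance, so when BSI rates differ between units its statistic is less variable under the null than assumed, and the test is conservative. A baseline variable that predicts BSI can also sharpen the treatment comparison, at no extra data collection.

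There is a pre-specification issue too. The Cox sentence neither includes nor excludes covariates. In an open-label trial (section 8.6), a model used if appropriate, with its terms unstated, leaves a choice to be made late. The SAP describes itself in section 5 as the detailed account of analyses that the protocol gives only in brief, so this is where the choice should be fixed.

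**Working it through.** **Inputs from the SAP.** Planned size: "The trial population aims to include 858 babies who require the narrowest PICC (Premicath 1" French). Allocation: "Babies will be randomised to AM-PICC or S-PICC in a ratio of 1:1", so 858/2 = 429 per arm. Test level: "All applicable statistical tests will be two-sided and will be performed using a 5% significance" level (section 12).

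**The plan's own figure.** The 858 cannot be rebuilt from this document, because section 10 defers it: "The sample size calculation can be found in section 9.4 of the protocol". That is normal and not a fault, but event rate, effect size and number of centres must therefore be assumed.

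**Orientation.** Assume a control risk of 15% and HR 0.6. Risk in the intervention arm = 1 - 0.85^0.6 = 0.093. Expected events = 429 × (0.150 + 0.093) = 104. Schoenfeld power = Φ(√(104/4) × |ln 0.6| - 1.96) = Φ(2.60 - 1.96) = 0.74. Across control risks of 10 to 20% and HRs of 0.5 to 0.7, power runs from 0.33 to 0.98, so the planned power cannot be inferred.

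**Simulation 1: time to event.** 858 babies, blocks of 4 within centre, control risk 15%, conditional HR 0.6, about 102 events, 1500 runs per row. Monte Carlo error is about √(0.7 × 0.3/1500) = 1.2 points per power figure. Score SD is the log-hazard SD of one baseline prognostic score. The last column adjusts for that score without stratifying by centre.

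| Centres | Score SD | Centre SD | Log-rank | Centre-stratified log-rank | Cox adjusted for score |
|---|---|---|---|---|---|
| 10 | 0 | 0 | 0.725 | 0.706 | 0.720 |
| 10 | 0.4 | 0.3 | 0.687 | 0.679 | 0.693 |
| 10 | 0.7 | 0.3 | 0.676 | 0.675 | 0.697 |
| 10 | 1.0 | 0.5 | 0.586 | 0.583 | 0.665 |
| 18 | 0 | 0 | 0.720 | 0.704 | 0.715 |
| 18 | 0.4 | 0.3 | 0.708 | 0.697 | 0.705 |
| 18 | 0.7 | 0.3 | 0.673 | 0.661 | 0.689 |
| 18 | 1.0 | 0.5 | 0.603 | 0.597 | 0.697 |

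Centre stratification changes power by -1.9 to -0.1 points. Adjustment changes it by -0.5 to +0.6 for a null or weak score, +1.6 to +2.1 for a moderate one and +7.9 to +9.4 for a strong one.

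**Simulation 2: larger centre effects.** HR 0.6, about 105 to 117 events, 2000 runs per cell. Centre stratification gives +1 to +2 points at SD 0.6, +2 (10 centres) and +4 (18 centres) at SD 0.8, and +2.5 and +3.6 at SD 0.9.

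**Type I error.** In simulation 1 with 18 centres, the unstratified log-rank rejected 5.0% of the time at centre SD 0.5 and 3.7% at SD 0.8; the stratified test gave 5.7% and 4.7%. Monte Carlo error is √(0.05 × 0.95/1500) = 0.6 points. In simulation 2 at centre SD 0.9, the unstratified test rejected 3.8 to 4.0% of the time.

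**Binary outcomes** (18 centres, 2000 runs). A centre-stratified Mantel-Haenszel test against chi-square gave 0 to +1 point (0.763 to 0.764 with no effects; 0.683 to 0.692 with score SD 1.0 and centre SD 0.5). Logistic regression adjusted for the score, against Fisher, gave +4 to +6 points for score SD 0.7 to 1.0, and +15 for SD 1.5 at 30% risk. About 2 of those points are Fisher's own conservatism.

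**Hazard ratio.** With score SD 1.0, the average unadjusted HR was 0.633 to 0.638, against 0.605 to 0.612 adjusted and a true conditional value of 0.60.

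**The case against.** The strongest reply is that the planned analysis is valid and the gain unproven. The SAP gives no number of centres, event rate or predictor strength. A centre SD of 0.6 to 0.9 means a central 95% range of hazards between units of exp(3.92 × 0.6) ≈ 10-fold to exp(3.92 × 0.9) ≈ 34-fold, and a predictor SD of 1.0 means exp(3.92) ≈ 50-fold. Nothing in the document establishes such ranges. This stands: the power loss is possible, not shown.

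An adjusted HR also answers a different question. The HR is non-collapsible, so at least part of the gap between 0.63 and 0.61 is the difference between a marginal and a conditional quantity, not bias. This stands and should be stated in the report. The Cox model also relies on proportional hazards, which section 17.4.1.2 itself doubts; keeping a log-rank test as the primary test limits that dependence.

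Timing counts as well. Section 19.1.1 shows that a blind review has taken place, and section 13.1 plans a formal interim analysis of the primary outcome. The change is therefore more than a line of code and must be dated and made without sight of allocation.

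A reader might infer from the uncited reference on covariate selection that an adjusted analysis was dropped. The document does not support that: in the visible text only reference 7 carries a citation mark, so an uncited entry shows little.

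**Conclusion.** The mismatch between design and analysis is clear from the text. Its consequence is modest and conditional: about -2 to 0 points of power from centre stratification if the centre SD is at most 0.5, +1 to +4 if it is 0.6 to 0.9, and from covariate adjustment about 0 to 2 points for weak to moderate predictors and 8 to 9 for a strong one. All these rest on an assumed event rate, HR, number of centres, block size and predictor strength.

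Two stronger readings are tempting. One is that ignoring the stratification factor makes the test invalid; it does not, since the error is towards conservatism and false positives are not inflated. The other is that the plan certainly wastes power by omitting strong predictors; the SAP gives no prognostic strength for any factor, so this cannot be asserted. The change is worth making because it aligns the analysis with the design, fixes the model in advance and has a small, bounded cost.

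**What to change.** Before allocations are requested:

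- Stratify the primary log-rank test and Cox model by centre. Pool centres with few events by a rule set in advance on event counts with arms combined, so that it can be applied blind.
- Pre-specify a Cox model stratified by centre and adjusted for gestational age and age at randomisation, both continuous. Report the unadjusted HR alongside, and state that the adjusted HR is conditional and the unadjusted one marginal.
- Include prior positive culture only with a note on section 17.4.1.1. A same-isolate culture less than 14 days after an earlier positive is not counted. For a culture taken in the 72 hours before randomisation, that exclusion lasts until 11 to 14 days after randomisation (14 - 3 = 11), so the rule itself removes some later positives from the endpoint.
- For common binary outcomes, give a centre-stratified Mantel-Haenszel relative risk. Keep Fisher's exact test for rare ones such as rifampicin resistance.
- State which form of the test the interim analysis uses.

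The cost is a dated SAP amendment, the pooling rule, and up to about 2 points of power if centres do not differ. No new data are needed.
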